7.2 Statistical Methods

The primary analysis will be based on a 1-df likelihood ratio test (LRT) of the null hypothesis that the 6 calendar month SCD mortality rate is identical for subjects randomized to WCD versus non-WCD (i.e. odds ratio of 1), conditional on enrolling site and date of enrollment (stratification variables that define randomized blocks), and further

parametrically adjusted for five additional pre-specified risk factors via conditional logistic regression (CLR):

- age (continuous, and flexibly modeled via a 4-df continuous piecewise linear spline with knots at 60, 70, and 80 years of age, allowing for a separate odds ratio per year within each decade of age),
- ejection fraction (continuous, and modeled via a 2-df continuous piecewise linear spline with a knot at 50%, allowing for a separate odds ratio per year above and below 50%, given that it is expected that mortality risk likely decreases smoothly up to about 50% but then perhaps levels off thereafter),
- race/ethnicity (binary: white non-Hispanics versus all others),
- diabetes (binary: yes versus no),
- myocardial infarction (binary: yes versus none),
- dialysis access (binary: catheter versus no catheter).

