The adjusted odds ratio (OR) for WCD along with its corresponding 95% confidence interval (CI) will be estimated via CLR. Note that, in stark contrast to case-control studies, there is essentially no loss of efficiency due to heavy stratification resulting in a large number of strata, provided almost every stratum contains at least 1 patient from each group (WCD, non-WCD). This condition is guaranteed, given the plan to stratify on only those variables defining blocks for randomization. This was verified by simulation and supported by results in DeStavola and Cox, which states that there is no loss of efficiency if the strata are perfectly balanced (e.g. via stratified randomization).³⁹ Thus, there is no concern of “over-stratifying,” even if SCD were independent of enrolling site and date of enrollment. In fact, in order for CLR to be computationally feasible it is necessary that no stratum be too large. Furthermore, even if SCD were independent of some or all of the 5 variables (8 df) parametrically adjusted for, the loss of efficiency and precision would be negligible since randomized treatment is completely independent of all risk factors. On the other hand, to the extent that SCD is associated with any of the adjustment or stratification variables, failing to control for them at the analysis stage could result in a substantial loss of efficiency. Standard power calculations assume that subjects are independent and identically distributed, at least given the adjustments, but this assumption would be violated if important predictors of SCD were not controlled for, thus resulting in lower power than that suggested by standard sample size and power calculations.

Exploratory analysis of the secondary endpoint of all-cause mortality will be based on a single 2-sided nominal 0.05 level LRT, using the same CLR method as used to analyze SCD, with whatever sample size (650, 975, or 1300 patients per arm) happens to be available when the trial ends. A simple nominal 0.05 level test will be performed for the analysis of all-cause mortality, treating the resulting data as a fixed sample size.

Secondary analyses will test interactions between WCD and SCD risk factors in order to investigate whether there are subgroups for whom WCD might be especially effective. Interactions between pairs of SCD risk factors will also be explored in secondary analyses.

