7.3 Group Sequential Design

Standard group sequential methods³⁸ can be applied, given the large-sample approximate normality of the estimated log(OR), and PASS 11 software was used to compute the alpha and power values for our custom group sequential stopping rule. We plan to conduct 2

interim analyses once the 6 calendar month SCD outcome has been observed for 1/2 and 3/4 of the subjects. Our custom stopping boundaries retain 4% nominal alpha for the third and final look, provided the study doesn't stop early, while testing each of the 2 interim analyses at the nominal alpha level of 0.01375 (see Table 4). The overall alpha level for the study is .05.

Table 4: Group sequential design for the two-arm randomized clinical trial.

Look	Relative Information	# WCD subjects	# non-WCD subjects	# Total subjects	Nominal Alpha	Corrected Alpha
1	50%	650	650	1,300	0.01375	0.01375
2	75%	975	975	1,950	0.01375	0.02231
3	100%	1,300	1,300	2,600	0.04000	0.05000

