7.4 Sample Size and Power

Although the odds ratio (OR) is the canonical parameter for our CLR analysis, we have specified power here in terms of the relative risk (RR), which is generally easier to interpret. As is well known, the OR will always be more extreme than the RR, though not by much if the outcome is rare in both groups (as it is here) or if the effect size is small.

This study is designed to provide 91% power to detect RR = 0.40 (OR = 0.39), assuming the SCD rate in the non-WCD arm is 3.5%. Our group sequential design increases the maximum sample size by just 4%, relative to a non-sequential study (1,250 per arm), while yielding—if the true RR = 0.40—a 36% reduction in expected sample size (804 per arm), as there is 69% chance of stopping early, and 46% chance of stopping at the very first look with just 650 subjects per arm.

Power is tabulated in Table 5 for 9 scenarios, varying the RR (.30, .40, .50) as well as the SCD mortality rate among controls (3.0%, 3.5%, 4.0%).

Table 5: Power as a function of RR and the SCD rate in the control arm.

Power (%) at Look 3	Power (%) at Look 2	Power (%) at Look 1	% SCD (WCD)	% SCD (non-WCD)	Absolute Reduction in % SCD	Relative Risk (RR)
96	80	57	0.90	3.00	2.10	0.30
85	60	38	1.20	3.00	1.80	0.40
67	40	23	1.50	3.00	1.50	0.50
98	87	66	1.05	3.50	2.45	0.30
91	69	46	1.40	3.50	2.10	0.40
74	47	28	1.75	3.50	1.75	0.50
99	92	73	1.20	4.00	2.80	0.30
94	76	53	1.60	4.00	2.40	0.40
80	54	33	2.00	4.00	2.00	0.50

A relative risk of 0.50 (OR = 0.49), i.e. a relative reduction of 50% and an absolute reduction of 1.75% in SCD, corresponds with a 12.5% reduction in all-cause mortality due to WCD,

assuming the all-cause mortality rate is 14% with about 25% of deaths attributable to SCD (3.5% SCD rate). Even under these conservative assumptions, our study maintains 74% power, as shown in Table 5. We believe that the risk reduction will be higher (at least 60% reduction in SCD, corresponding with at least a 15% reduction in all-cause mortality), thus providing 91% power. Furthermore, this study maintains 85% power to detect $RR = 0.40$ ($OR = 0.39$) even if the SCD rate were only 3% (rather than 3.5%) among controls.

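### Section 7.2 counts five covariates and 8 df but lists six and 10 df; under either count the adjusted test slightly exceeds the stated overall alpha of 0.05

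*Combined protocol and SAP*

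**What the plan says.** Section 7.2 defines the primary test as a 1-df likelihood ratio test from a conditional logistic model with the randomisation blocks as strata, "parametrically adjusted for five additional pre-specified risk factors via conditional logistic regression (CLR". The bullets that follow name six variables: age, EF, race/ethnicity, diabetes, myocardial infarction and dialysis access. EF has its own bullet, "ejection fraction (continuous, and modeled via a 2-df continuous piecewise linear spline with a knot at 50" percent, "allowing for a separate odds ratio per year above and below 50" percent. Later in the section the count is repeated, with the claim that adjustment costs little: "some or all of the 5 variables (8 df) parametrically adjusted for, the loss of efficiency and precision would be negligible".

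On the heavy stratification, the section says "This was verified by simulation and supported by results in" a published paper. That check is described only for loss of efficiency.

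Section 7.3 applies standard group sequential methods "given the large-sample approximate normality of the estimated log(OR" and tests at nominal 0.01375, 0.01375 and 0.04. It concludes: "The overall alpha level for the study is .05". Section 7.4 gives a "46% chance of stopping at the very first look with just 650 subjects per arm" if the true relative risk is 0.40. Section 7.6 promises a stagewise estimate of the odds ratio that is equally likely to fall on either side of the true value.

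**The concern.** There are two linked problems.

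First, the count and the list disagree about the confirmatory model, which also decides early stopping. The disagreement is exactly the EF term, so the text does not say with one voice whether EF is in the model.

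Second, the boundaries rest on large-sample normality, but the adjusted test is applied when deaths are few relative to the parameters fitted. In that setting a likelihood ratio test tends to reject too often, and a fitted odds ratio tends to lie too far from 1. The documents describe no check of either for the adjusted test. At stake are the stated 5% error rate, the error spent at the first look, and the centring of the reported odds ratio.

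**Working it through.** **1. Covariate count (Section 7.2 bullets).** Age 4, EF 2, race/ethnicity 1, diabetes 1, myocardial infarction 1, access 1.
- All six: 4+2+1+1+1+1 = 10 df.
- Without EF: 4+1+1+1+1 = 8 df over five variables, which is the stated count.

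**2. The plan's own figures.** Information fractions are t = 0.50, 0.75, 1 and corr(Z_i, Z_j) = sqrt(t_i/t_j). The two-sided critical values are 2.464, 2.464 and 2.054.
- Trivariate normal integration gives cumulative alpha 0.01375 / 0.02231 / 0.05000, matching Table 4.
- For power at 3.5% against 1.4%: log OR = ln[(0.014×0.965)/(0.035×0.986)] = -0.938. SE at 1,300 per arm = sqrt[1/(1,300×0.035×0.965) + 1/(1,300×0.014×0.986)] = 0.280, so the drift is 3.35 in size. Cumulative power is 46.1 / 69.4 / 90.8%, against 46 / 69 / 91% in Table 5.

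So the boundaries are right under asymptotic normality.

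**3. Events available at look 1 (650 per arm).**
- Null, 3.5% in both arms: 650×0.07 = 45.5 deaths.
- Relative risk 0.40: 650×(0.035+0.014) = 31.9 deaths.
- With treatment plus 10 df (11 parameters), that is 4.1 and 2.9 deaths per parameter. With 8 df (9 parameters) it is 5.1 and 3.5.

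**4. Simulated overall alpha at the stated boundaries.** Random 4- and 6-blocks within site, exact conditional likelihood per block, 1-df likelihood ratio test on the first 1,300, 1,950 and 2,600 subjects. The same trials were analysed three ways. Monte Carlo SE is about 0.001-0.002.

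| Null scenario | Trials | Treatment only | 8 df | 10 df |
|---|---|---|---|---|
| 3.5%, no effects | 30,000 | 0.0515 | 0.0578 | 0.0600 |
| 3.5%, effects A | 30,000 | 0.0525 | 0.0590 | 0.0606 |
| 3.5%, A, 100 sites, site SD 0.5 | 18,000 | 0.0526 | 0.0574 | 0.0589 |
| 3.5%, A doubled | 15,000 | 0.0489 | 0.0545 | 0.0570 |
| 3.5%, effects B, 100 sites | 40,000 | 0.0518 | 0.0571 | 0.0588 |
| 3.5%, effects B, 200 sites | 20,000 | 0.0500 | 0.0568 | 0.0591 |
| 3.5%, no effects, 100 sites | 20,000 | 0.0480 | 0.0538 | 0.0566 |
| 3.5%, no effects, 150 sites | 20,000 | 0.054 | 0.058 | 0.061 |
| 2.45%, effects B, 100 sites | 20,000 | 0.0516 | 0.0613 | 0.0643 |

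On the same trials at 3.5%, the adjusted test rejects 0.4 points (0.058-0.054) to 0.9 points (0.0591-0.0500) more often than treatment alone. Look 1 spends about 0.017-0.019, against 0.01375 stated and 0.013-0.015 with treatment alone. Two further 10-df runs at 2.45% gave 0.063 and 0.0655.

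Assumptions not in the documents:
- *A:* age N(66,10) on 50-92; EF N(56,9) on 36-78; white 50%, diabetes 50%, infarction 15%, catheter 75%; log-odds 0.025 per year of age, -0.02 per EF point below 50, and 0.3, 0.4, 0.4 for diabetes, infarction, catheter.
- *B:* age N(66,11) on 50-95; EF N(56,9) on 35-80; prevalences 45, 55, 15, 75%; log-odds 0.35 per decade of age, -0.3 per 10 EF points below 50, and 0.2, 0.2, 0.4, 0.4 for the four binaries.

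**5. Odds ratio when the true value is 0.391.** Median over all simulated trials, whether or not they stop, at looks 1/2/3:
- 10 df: 0.33-0.34 / 0.36 / 0.37
- 8 df: 0.35 / 0.37 / 0.37
- treatment only: 0.39

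Under the null the odds ratio is centred on 1.

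**6. The quoted efficiency claim (no covariate effects).** Spread of log OR, 10 df against treatment only:
- Look 1: 0.361/0.318 = 1.14 (null) and 0.530/0.424 = 1.25 (relative risk 0.40).
- Look 3: 0.230/0.219 = 1.05 and 0.317/0.292 = 1.09.

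At matched alpha, final power is 92% against 93%.

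**The case against.** **EF is fully specified.** A reader might infer that the sponsor could decide on EF after seeing the data. The documents do not support that. EF has its own bullet with df, knot and a clinical rationale, and the natural reading is that the tally is out of date. Including EF moves alpha by only about 0.002-0.003. This part is a correction of wording.

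**Table 4 is not miscalculated.** A reader might infer that it is. It reproduces exactly, and Section 7.3 openly calls its basis approximate. What remains is that the approximation is a little optimistic for this test.

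**The quoted sentence is about efficiency and precision, not type I error.** That is correct. At the final look it nearly holds. It is weaker for precision at look 1, although that spread is taken over all trials, which the plan does not report.

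**Not all of the excess over 0.05 comes from the covariates.** That is also correct: treatment alone runs from 0.048 to 0.054. The paired difference of 0.4-0.9 points is the sturdier figure, and the lower end for 8 df (0.0538) is soft.

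**The stagewise estimate.** In one simulation it exaggerated benefit in 57-62% of trials, against 50-53% with treatment alone. The range depends on how standard errors and stopping are entered, so only the direction should be relied on.

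**Conclusion.** The count mismatch is certain from the text. The excess error is real and modest: about 0.4-0.9 points over the unadjusted test at a 3.5% rate, giving overall alpha of about 0.054-0.059 (8 df) or 0.057-0.061 (10 df). It grows as deaths become fewer. It appears even when covariates have no effect, so it does not need assumed effect sizes, but the decimals depend on assumed covariate distributions. Because both counts are affected, correcting the tally alone does not restore 0.05. If the device works, the equal-chance property claimed in Section 7.6 holds only approximately, with the error towards exaggerated benefit. Power is not harmed. The plan should be changed, but the point does not undermine the design.

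**What to change.** 1. Make Section 7.2 agree on one primary model: six variables and 10 df as listed, or five and 8 df without EF. Give EF slopes per percentage point.
2. Before unblinding, extend the sponsor's simulation to type I error and odds-ratio bias at each look, over a range of SCD rates (for example 2-4%).
3. Then either calibrate the nominal levels to an overall 0.05 over that range, or take the p-value from a within-block re-randomisation of the same statistic. Restate Tables 4 and 5 and the p-value ranges in Section 7.6.
4. Feed a bias-reduced (Firth-type) conditional fit into the stagewise estimate, or state the remaining bias. In simulation, Firth inputs brought the share of exaggerated estimates from 61-62% to 53-54%.

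For illustration at 3.5% only, levels of 0.011/0.011/0.0325 with 10 df give alpha of about 0.047-0.050 and cumulative power of about 45/70/91%. They should not be written into the plan as they stand: they give alpha of about 0.052 at 3.0% and 0.051-0.055 at 2.45%.

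The cost is SAP wording and a simulation rerun, with no new data. At relative risk 0.40, these levels raise simulated mean size from 905-911 to 924-930 per arm, about 20 more. The 804 per arm in Section 7.4 is not used as the baseline, because the stated stopping chances imply 650×0.46 + 975×0.23 + 1,300×0.31 = 926.

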7.3 Group Sequential Design

Standard group sequential methods³⁸ can be applied, given the large-sample approximate normality of the estimated log(OR), and PASS 11 software was used to compute the alpha and power values for our custom group sequential stopping rule. We plan to conduct 2

interim analyses once the 6 calendar month SCD outcome has been observed for 1/2 and 3/4 of the subjects. Our custom stopping boundaries retain 4% nominal alpha for the third and final look, provided the study doesn't stop early, while testing each of the 2 interim analyses at the nominal alpha level of 0.01375 (see Table 4). The overall alpha level for the study is .05.

Table 4: Group sequential design for the two-arm randomized clinical trial.

Look	Relative Information	# WCD subjects	# non-WCD subjects	# Total subjects	Nominal Alpha	Corrected Alpha
1	50%	650	650	1,300	0.01375	0.01375
2	75%	975	975	1,950	0.01375	0.02231
3	100%	1,300	1,300	2,600	0.04000	0.05000

7.4 Sample Size and Power

Although the odds ratio (OR) is the canonical parameter for our CLR analysis, we have specified power here in terms of the relative risk (RR), which is generally easier to interpret. As is well known, the OR will always be more extreme than the RR, though not by much if the outcome is rare in both groups (as it is here) or if the effect size is small.

This study is designed to provide 91% power to detect RR = 0.40 (OR = 0.39), assuming the SCD rate in the non-WCD arm is 3.5%. Our group sequential design increases the maximum sample size by just 4%, relative to a non-sequential study (1,250 per arm), while yielding—if the true RR = 0.40—a 36% reduction in expected sample size (804 per arm), as there is 69% chance of stopping early, and 46% chance of stopping at the very first look with just 650 subjects per arm.

Power is tabulated in Table 5 for 9 scenarios, varying the RR (.30, .40, .50) as well as the SCD mortality rate among controls (3.0%, 3.5%, 4.0%).

Table 5: Power as a function of RR and the SCD rate in the control arm.

Power (%) at Look 3	Power (%) at Look 2	Power (%) at Look 1	% SCD (WCD)	% SCD (non-WCD)	Absolute Reduction in % SCD	Relative Risk (RR)
96	80	57	0.90	3.00	2.10	0.30
85	60	38	1.20	3.00	1.80	0.40
67	40	23	1.50	3.00	1.50	0.50
98	87	66	1.05	3.50	2.45	0.30
91	69	46	1.40	3.50	2.10	0.40
74	47	28	1.75	3.50	1.75	0.50
99	92	73	1.20	4.00	2.80	0.30
94	76	53	1.60	4.00	2.40	0.40
80	54	33	2.00	4.00	2.00	0.50

A relative risk of 0.50 (OR = 0.49), i.e. a relative reduction of 50% and an absolute reduction of 1.75% in SCD, corresponds with a 12.5% reduction in all-cause mortality due to WCD,

assuming the all-cause mortality rate is 14% with about 25% of deaths attributable to SCD (3.5% SCD rate). Even under these conservative assumptions, our study maintains 74% power, as shown in Table 5. We believe that the risk reduction will be higher (at least 60% reduction in SCD, corresponding with at least a 15% reduction in all-cause mortality), thus providing 91% power. Furthermore, this study maintains 85% power to detect $RR = 0.40$ ($OR = 0.39$) even if the SCD rate were only 3% (rather than 3.5%) among controls.

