7. STUDY DESIGN

This study will employ a group sequential two-arm randomized clinical trial to test the hypothesis that the wearable cardioverter defibrillator (WCD) reduces overall mortality within a 6 calendar month period beginning at the time of randomization, which is to occur no later than 2 calendar months after the initiation of hemodialysis.

Enrolled subjects will be 1:1 randomized to WCD or non-WCD, stratified by enrolling site and, implicitly, by calendar time of enrollment. All subjects will be followed for at least 6 calendar months regardless of compliance. The primary endpoint is the binary event of whether or not sudden cardiac death occurs within the 6 month follow-up period. The primary analysis will be an intention-to-treat analysis based on the randomization, ignoring the fact that some subjects randomized to WCD may discontinue use of the device early while some subjects randomized to the non-WCD arm may obtain and wear a WCD.

Overall mortality at 6 calendar months in the non-WCD arm is expected to be 14%, with one quarter of all deaths due to sudden cardiac death (SCD rate of 3.5%).² Taking some anticipated noncompliance into consideration, as some subjects are expected to discontinue WCD prior to 6 months, we hypothesize that the WCD will provide a relative reduction in SCD of 60%. Thus, we

expect an absolute reduction of 2.1% in SCD mortality, corresponding to a relative risk (RR) of 0.40 and an odds ratio (OR) of 0.39.

The exact number of subjects to be randomized is uncertain since the group sequential trial was designed to have 46% power to stop at the first interim look at 650 (50%) subjects per arm, and 69% power to stop at the second interim look at 975 (75%) subjects per arm, while controlling the overall significance level at $\alpha = 0.05$. But if the study continues to the third and final look, a maximum of 1,300 subjects will be enrolled in each arm, for a total of 2,600 subjects providing 91% power to detect the hypothesized 60% relative reduction in overall 6-month SCD mortality from 3.5% down to 1.4%.

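### The expected sample size at RR = 0.40 (804 per arm, a 36% saving) contradicts the plan's own stopping probabilities, which give about 926 per arm, a 26% saving.

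*Combined protocol and SAP*

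**What the plan says.** Section 7.4 says that the sequential design raises the maximum sample size by 4% "relative to a non-sequential study (1,250 per arm"), and that in return, if the true RR is 0.40, it brings a "36% reduction in expected sample size (804 per arm), as there is 69% chance of stopping early, and 46% chance of stopping at" the first look, at 650 per arm. The stopping probabilities are offered as the reason for the 804.

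Section 7 gives the same probabilities. For the first look it states "46% power to stop at the first interim look at 650 (50%) subjects per arm"; its figure for the second look, with 975 per arm, is again 69%. It adds: "But if the study continues to the third and final look, a maximum of 1,300 subjects will be enrolled in each arm", with 91% power at that point. The row of Table 5 for RR = 0.40 and a 3.5% control rate repeats 46%, 69% and 91%. Table 4 places the looks at 650, 975 and 1,300 per arm. Sections 7.3 and 7.6 describe early stopping only on crossing the significance boundary.

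**The concern.** An expected sample size is a weighted average of the sizes at the looks, and the weights are the chances of stopping there. Every input needed stands in the plan, and most stand in the same sentence as the 804. A 31% chance of running to 1,300 per arm, with fewer than half of trials stopping at 650, looks too heavy for an average of 804.

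At stake is a stated property of the design. The protocol sets the saving against a 4% larger maximum, at its own design effect. A reader planning enrolment, duration or device supply from the expected size would work with too small a number.

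**Working it through.** **Inputs**
- Looks at 650, 975 and 1,300 per arm (Table 4).
- Cumulative stopping probabilities at RR = 0.40 and a 3.5% control rate: p1 = 0.46 by look 1 and p2 = 0.69 by look 2 (Sections 7 and 7.4, Table 5).
- Comparator: 1,250 per arm (Section 7.4).
- Two-sided nominal alpha of 0.01375, 0.01375 and 0.04 (Section 7.3).

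**1. The plan's figures that reproduce.** The log odds ratio for 1.4% against 3.5% is ln[(0.014/0.986)/(0.035/0.965)] = −0.938. At 650 per arm its variance is [1/(0.014 × 0.986) + 1/(0.035 × 0.965)]/650 = 102.05/650 = 0.157, so the standard error is 0.396 and the standardised effect is 2.367. The critical value for 0.01375 two-sided is 2.464. Power at look 1 is therefore Φ(2.367 − 2.464) = 46.1%.

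Integrating the joint normal distribution over all three looks gives:

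| | Look 1 | Look 2 | Look 3 |
|---|---|---|---|
| Cumulative alpha, computed | 0.01375 | 0.02231 | 0.0500 |
| Cumulative alpha, Table 4 | 0.01375 | 0.02231 | 0.05000 |
| Cumulative power, computed | 46.1% | 69.4% | 90.8% |
| Cumulative power, stated | 46% | 69% | 91% |

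The probabilities at the design effect are sound. The maximum also agrees with its comparator (1,300/1,250 = 1.04), and the 36% follows from 804 (1 − 804/1,250 = 35.7%). The 36% and the 804 therefore agree with each other, and any error in one carries to the other.

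**2. Expected size from the stated probabilities.**

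E[N] per arm = 650·p1 + 975·(p2 − p1) + 1,300·(1 − p2) = 1,300 − 325·(p1 + p2)

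= 650 × 0.46 + 975 × 0.23 + 1,300 × 0.31

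= 299 + 224.25 + 403 = **926.25**

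Saving: 1 − 926.25/1,250 = **25.9%**. With the unrounded probabilities from step 1 the result is 924.5, a saving of 26.0%.

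**3. Rounding.** With p1 = 0.465 and p2 = 0.695, E[N] = 923.0 (26.2%). With p1 = 0.455 and p2 = 0.685, E[N] = 929.5 (25.6%). To reach 804, p1 + p2 would have to be (1,300 − 804)/325 = 1.526; the plan's sum is 1.15.

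**4. A floor from the 69% alone.** If every early stop came at look 1, E[N] = 0.69 × 650 + 0.31 × 1,300 = 851.5, or 848.25 with p2 = 0.695. The value 804 lies below both.

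**5. Where 804 might come from.** This is inference; the documents do not show it.
- Weighting look 3 by the chance of rejecting there, instead of the chance of reaching it, gives 804.5 with the unrounded probabilities (809.25 with the rounded ones: 299 + 224.25 + 1,300 × 0.22). That leaves out the roughly 9% of trials that run to 1,300 per arm without rejecting, worth 0.092 × 1,300 ≈ 120 per arm.
- The RR = 0.30 row of Table 5 at a 3.5% control rate (66% and 87%) gives 1,300 − 325 × 1.53 = 802.75, a saving of 35.8%.

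Neither is an expected sample size at RR = 0.40. The same formula at RR = 0.40 with control rates of 3.0% and 4.0% gives 981.5 and 880.75, so no RR = 0.40 row of Table 5 yields 804.

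**The case against.** The best defence is that 804 rests on a reading other than the one used here. Four were tried.

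- *The 69% is conditional on passing look 1.* The wording in Section 7 taken alone might allow this, but Section 7.4 calls it the chance of stopping early, and the design reproduces it as cumulative. Read as conditional it gives 299 + 975 × 0.54 × 0.69 + 1,300 × 0.54 × 0.31 = 880, still not 804.
- *The saving is against the 1,300 maximum.* The plan names 1,250. Against 1,300, 926 saves 28.8%.
- *A futility stop lowers the average.* None is described. Since 69% is given as the whole chance of stopping early, the floor of 851.5 holds whatever the reason for stopping.
- *The average covers successful trials only.* This gives 809.25/0.91 = 889 per arm.

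Two points on the other side stand. First, the figure is descriptive: the maximum sample size, boundaries, alpha, power and analysis do not use it, and the study size in Section 5 rests on the range of 1,300 to 2,600. Second, 926 is not exact for subjects enrolled. It comes from rounded percentages (924.5 unrounded), and Section 7.3 times each interim look after 6-month outcomes are in. If enrolment continues meanwhile, an early stop could come with more than 650 or 975 per arm enrolled. That moves the enrolled number further from 804, not closer.

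**Conclusion.** The concern holds. The plan's 46% and 69% cannot be reconciled with 804 per arm. They give about 926 per arm, about 1,850 in total against the 1,608 implied (2 × 926.25 − 2 × 804 ≈ 244 more subjects), and the saving is overstated by about 10 percentage points. The conclusion assumes the stated look sizes, cumulative probabilities and no futility stop; the 851.5 floor needs only the look sizes and the 69%. The severity is minor: a stated design property is wrong, but the design itself reproduces and is unaffected. The cause of the error is unknown, and the conclusion does not depend on it.

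**What to change.** In Section 7.4, change the 36% reduction to 26% and the 804 per arm to about 926 per arm, and state that this counts subjects with a 6-month outcome at the stopping look. If the sponsor re-runs the design software, the unrounded figure should be about 925; the saving is 26% either way. The 46%, 69% and 91% can stay.

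The cost is one sentence and a less favourable figure. Nothing else in the design or analysis changes.

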5. STUDY SIZE

A minimum of 1,300 and a maximum of 2,600 subjects will be enrolled into this study. A maximum of 200 sites will enroll patients into the trial.

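### The looks wait for 6-month outcomes, so 650 and 975 per arm are numbers analysed; unless enrolment is paused, more subjects will have been randomised at an early stop than the plan states

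*Combined protocol and SAP*

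**What the plan says.** Section 7.3 times the two interim analyses by completed outcomes: they take place "once the 6 calendar month SCD outcome has been observed for 1/2 and 3/4 of the subjects". Table 4 puts these looks at 1,300 and 1,950 subjects in total (650 and 975 per arm).

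Other sections use the same counts for the size of the trial if it stops there:

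- Section 7 ties them to randomisation: "The exact number of subjects to be randomized is uncertain since the group sequential trial was designed to have 46% power to stop" at 650 per arm, with "69% power to stop at the second interim look at 975 (75%) subjects per arm". If neither look stops the trial, "a maximum of 1,300 subjects will be enrolled in each arm, for a total of 2,600 subjects providing 91% power".
- Section 7.2 says the all-cause mortality analysis will use the sample available at the end of the trial, and allows only three sizes: 650, 975 or 1,300 per arm.
- Section 7.4 compares an expected 804 per arm with 1,250 for a non-sequential study, and supports the saving with a "46% chance of stopping at the very first look with just 650 subjects per arm".
- Section 5 gives the range: "A minimum of 1,300 and a maximum of 2,600 subjects will be enrolled into this study".

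No section says whether enrolment continues, slows or stops while outcomes mature, and none gives an accrual rate. Section 7 does require every subject to be followed for at least 6 months.

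**The concern.** A subject's outcome is known about six months after randomisation. When the 1,300th outcome is in, everyone randomised during the preceding six months is also in the trial. The number analysed equals the number randomised only if enrolment was held over that period. The plan makes no provision for a hold, yet it treats the two numbers as one.

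Two things are at stake. First, the saving in subjects is the advantage that Section 7.4 claims for the sequential design, and it is overstated to the extent that enrolment runs on. An IRB or DSMB reader would take a look-1 stop to mean about 1,300 people randomised. Second, the subjects beyond the look size will have 6-month outcomes, but the sample sizes listed in Section 7.2 leave no place for them.

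**Working it through.** **Step 1. Reproduce the plan's figures.** Inputs: SCD 3.5% versus 1.4%, 1,300 per arm at the final look, information 0.50, 0.75 and 1, and two-sided nominal alphas 0.01375, 0.01375 and 0.04 (Sections 7, 7.3 and 7.6).

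- Drift = log(OR)/SE, with SE² = 1/(1,300 × 0.035 × 0.965) + 1/(1,300 × 0.014 × 0.986) = 0.0785. The absolute log(OR) is 0.938 and the drift is 3.35.
- Cumulative alpha under the null: 0.01375, 0.02231, 0.05000, as in Table 4.
- Cumulative power: 46.1%, 69.4%, 90.8%, against the stated 46%, 69% and 91%.

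The stopping probabilities are therefore sound inputs: 46% at look 1, 69% − 46% = 23% at look 2, and 31% going on to look 3.

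**Step 2. Baseline without overrun.** Expected per arm = 0.46 × 650 + 0.23 × 975 + 0.31 × 1,300 = 299 + 224.25 + 403 = 926. The saving is 1 − 926/1,250 = 26%. The printed 804 and 36% do not follow from these probabilities. That is a separate error, so the effect of overrun is measured from 26%, not from 36%.

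**Step 3. Add the six-month wait.** Let r be a steady monthly accrual. It is an assumption, because the documents give none. With no pause:

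- N1 = min(2,600, 1,300 + 6r)
- N2 = min(2,600, 1,950 + 6r)
- Expected randomised per arm = (0.46 × N1 + 0.23 × N2 + 0.31 × 2,600)/2

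Example at r = 100: (0.46 × 1,900 + 0.23 × 2,550 + 806)/2 = (874 + 586.5 + 806)/2 = 1,133. The saving is 1 − 1,133/1,250 = 9%.

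| Assumed r per month | Randomised at look 1 | Randomised at look 2 | Expected per arm | Saving against 1,250 |
|---|---|---|---|---|
| No overrun | 1,300 | 1,950 | 926 | 26% |
| 25 | 1,450 | 2,100 | 978 | 22% |
| 50 | 1,600 | 2,250 | 1,030 | 18% |
| 100 | 1,900 | 2,550 | 1,133 | 9% |
| 150 | 2,200 | 2,600 | 1,208 | 3% |
| 200 | 2,500 | 2,600 | 1,277 | none (2% more) |

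**Step 4. Thresholds.**

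- A look-2 stop avoids no randomisations once 1,950 + 6r ≥ 2,600, so r ≥ 650/6 = 108.3 per month. That rate would fill 2,600 in 24 months.
- The same holds for look 1 once r ≥ 1,300/6 = 216.7 per month.
- Below 108.3 per month, overrun adds 0.69 × 3r = 2.07r per arm. Half of the 324-per-arm saving (1,250 − 926) is lost at 162/2.07 = about 78 per month.

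**Step 5. Six months is a lower bound.** Visit 4 may fall up to 14 days late (Section 6.6), deaths go to adjudication (Section 7.1), and the DSMB validates the events used for stopping (Section 13). With a lag of 6.5 months, the look-2 threshold falls to 650/6.5 = 100 per month.

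**The case against.** The best defence is that 650 per arm is correct as the number analysed. It appears in a power section, Table 4 sets the counts beside relative information, and the power and alpha figures reproduce. The documents are also silent on enrolment during the wait: they do not say that it continues. With an unstated pause, 650 per arm would also be the number randomised. No accrual rate is given, so the size of the effect is conditional. At 50 per month about two thirds of the 26% saving remains.

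All of that stands, and it limits the point to labelling and to a missing operating rule. It does not remove the point. Section 7 speaks of the number to be randomised, Section 7.2 of the sample available at the end of the trial, and Section 7.4 of a saving in sample size against 1,250. If these numbers rest on a pause, the plan has to say so, because enrolment would be halted for about six months before each look. Without one, some overrun is unavoidable: even at 25 per month, when 2,600 would take 104 months, 150 extra subjects are randomised by look 1.

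A reader might also infer that the minimum of 1,300 in Section 5 is wrong. It is not: 1,300 + 6r is never below 1,300, so it remains true as a floor.

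**Conclusion.** The point holds as a mismatch between the count that triggers a look and the count described as randomised or available at a stop. Unless enrolment is held, a look-1 stop comes with 1,300 + 6r randomised, not 1,300. At RR 0.40 the expected saving falls from 26% to about 18%, 9% and 3% at 50, 100 and 150 per month. From about 108 per month a look-2 stop avoids no randomisations. These figures rest on steady accrual, a six-month lag, no pause and the plan's own stopping probabilities.

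Several stronger readings are tempting but unsupported:

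- That a look-1 stop cannot happen with 650 per arm randomised. The documents do not exclude a pause.
- That most of the saving is lost in practice. Nothing in the documents shows which rate to expect, and 200 sites is only a maximum.
- That the whole fall from 36% is due to overrun. The part from 36% to 26% belongs to the separate error in the 804.
- That the saving is the declared reason for the sequential design. Section 7.4 presents it as a result of the design.
- That the maximum exposure was understated. The 2,600 is disclosed throughout.
- That a late look 2 is of no use. The threshold concerns randomisations only.

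Type I error and power at the looks do not change.

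**What to change.** 1. In Table 4 and Sections 7 and 7.4, label the look counts as subjects with a completed 6-month outcome. In 7.4, describe the 650 per arm as the number analysed and drop the word suggesting that it is all who are involved.
2. In Sections 7 and 7.4, give the number randomised at a look-1 or look-2 stop as look size plus at least six months of accrual, to a maximum of 2,600. Give the expected number randomised and the saving on the same basis, over a range of assumed accrual rates. If a pause is intended, state it instead, with the delay that it adds at each look.
3. In Section 7.2, replace the three fixed sample sizes so that subjects randomised beyond the look size, who are followed for 6 months anyway, are included in the all-cause mortality analysis.

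Section 5 can stay as a range. If enrolment is not paused, the cost is wording only: the boundaries, alpha and maximum size do not change, but the stated saving becomes less favourable. If a pause is chosen, the cost is about six months of halted enrolment before each look.
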